5 DATA REVIEW AND QUALITY

5.1 Data Management

Study data will be entered and stored in a database using Electronic Data Capture (EDC). Data fields are reviewed, checked, and source verified by the data management function of the Sponsor, or the Sponsor-designated contract research organization (CRO) specializing in data management. Data quality reviews and checks are specified in the data management plan.

5.2 Electronic Data Transfer

For all statistical analyses, a snapshot of the data will be taken from the EDC database along with snapshots of data external to the EDC database, if applicable. This will allow reproducibility of the analyses. The data snapshots will be stored and transferred to the responsible statistician(s) and programmer(s) at the Sponsor, or the Sponsor-designated CRO.

5.3 Handling of Missing Data

In general, missing data will not be imputed. Incomplete dates (missing day or month) associated with AE and concomitant medication dates may be imputed.

5.4 Data Transformation

If required by the Sponsor, source data from the EDC may be programmatically transformed to datasets more amenable for statistical analysis. These may include data formats for regulatory submissions in the form of Study Data Tabulation Model (SDTM) and Analysis Data Model (ADaM). The statistical programs used to perform the transformation will be validated to ensure accuracy and no loss of content. Otherwise, raw and ADaM-like datasets will be utilized for reporting purposes including generation of TLFs.

5.5 Validation of Statistical Analyses and Outputs

Analysis programs will be developed in SAS v9.4 or later, unless otherwise specified. Other statistical software, such as R, may be used as appropriate. All analyses and outputs intended for the CSR will be validated following the CRO's standard operating procedures to ensure accuracy, traceability, and reproducibility.

6 STATISTICAL ANALYSES

This section describes the statistical analyses to be conducted in relation to the primary, secondary, and exploratory objectives of the study.

6.1 General Statistical Considerations

In general, all analyses will be summarized by dose level and study treatment (e.g. monotherapy, combination with cemiplimab). Safety analysis will be based on the safety analysis population. The primary efficacy analysis will be based on the efficacy evaluable population by study treatment and/or tumor indication.

For each tumor indication, subjects administered the same study treatment may be combined for analysis purposes, regardless of study phase. Statistical inference, when performed, will be assessed at the 2-sided nominal 5% significance level without multiplicity adjustment. Point estimates will be accompanied by 95% confidence intervals (CIs). For the ORR endpoint assessed per the Simon's 2-stage design, the 2-sided 80% CI may be used.

For continuous variables, the number of observations (n), mean, standard deviation, median, minimum, and maximum will be provided as summary statistics. The mean and median will be reported to one additional decimal place compared to the original data. The standard deviation will be reported to two additional decimal places compared to the original data and the minimum and maximum will be reported to the same number of decimal places as the original data.

For categorical variables, the frequency and percentage in each category will be displayed. Percentages (e.g., for AEs and concomitant medications) will be calculated out of the population total for each cohort. Footnotes will clarify the denominator used in each output if other than the analysis set stated in the title. Percentages will be reported to one decimal place throughout unless the percentage is 100 (in which case no decimal places will be presented) or if the frequency count is zero (in which case no percentage will be presented).

For time to event data, unless otherwise noted, the median value, 25th percentile and 75th percentile will be calculated using the Kaplan-Meier method. The Brookmeyer and Crowley method will be used to calculate the CI of the median value (Brookmeyer and Crowley 1982). Also, the Greenwood formula will be used to calculate the CI of the rate of interest pertaining to the time to event data, at a given time point estimated using the Kaplan-Meier method (Kalbfleisch and Prentice 2002). The time to event analysis will be calculated only if an adequate number of responses are observed to warrant.

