9.2.5. Efficacy analysis

The primary analysis for efficacy will be based on the cohort-specific efficacy evaluable analysis set. Sensitivity analysis may include pooling additional subjects treated in Phase 1 at the same dose level in the same tumor type.

For objective response rate (ORR), the Clopper-Pearson 80% and 95% confidence intervals (CIs) will be provided. Confidence intervals adjusting for the 2-stage nature of the design may also be provided.

Duration of response (DoR) will be calculated among responders (CR and PR). The Kaplan-Meier method will be used to estimate median DoR and the confidence intervals. Subjects who continue to respond at the time of the analysis will be censored at the last assessment of response.

Progression-free survival (PFS) is measured from the date of first study treatment dose until the first date when progressive disease (PD) is objectively documented or death from any cause. Subjects without PD or death will be censored at the last available tumor assessment. PFS will be summarized using the Kaplan-Meier method.

Overall survival (OS) is measured from the date of first study treatment dose until death. Subjects who are alive will be censored at the last known alive date. OS will be summarized using the Kaplan-Meier method.

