2.2 Study Objectives and Endpoints

The objectives of the study are to evaluate the safety, tolerability, preliminary efficacy, PK, and pharmacodynamics of E-602, as a single agent or in combination with cemiplimab, for the treatment of subjects with advanced tumors.

Table 2. Summary of Study Objectives and Endpoints

Objectives	Endpoints	
Dose Escalation Phase (Phase 1)		
Primary		
 To evaluate the safety and tolerability of E-602 as monotherapy in subjects with advanced cancers. To evaluate the safety and tolerability of E-602 in combination with cemiplimab in subjects with advanced cancers. 	 Incidence of adverse events (AEs) and serious adverse events (SAEs) graded according to National Cancer Institute (NCI) Common Terminology Criteria for Adverse Events (CTCAE) v5.0. Incidence and nature of dose limiting toxicities (DLTs) within a modified 3+3 trial design. 	
To determine the maximum tolerated dose (MTD) and/or recommended Phase 2 dose (RP2D) of E-602 as monotherapy.	The MTD and/or RP2D based on occurrence of DLTs within a modified 3+3 design.	
• To determine the MTD and/or RP2D of E-602 in combination with cemiplimab.		
Secondary		
 To assess the PK of E-602 as monotherapy. To assess the PK of E-602 in combination with cemiplimab. To evaluate the immunogenicity of E-602 	• Noncompartmental PK parameters of E-602 as monotherapy and in combination with cemiplimab, including the maximum plasma concentration (C _{max}) and area under the plasma concentration-time curve (AUC).	
To evaluate preliminary antitumor activity of E-602 as monotherapy in subjects with advanced cancers.	 Number and percentage of subjects who develop detectable antidrug antibodies (ADA). 	
To evaluate preliminary antitumor activity of E-602 in combination with cemiplimab in subjects with advanced cancers.	Objective response rate (ORR) of confirmed complete response (CR) and partial response (PR) using RECIST v1.1 and iRECIST.	
	• Duration of response (DoR).	
	 Progression-free survival (PFS), defined as the time from the first dose to first evidence of radiographically detectable disease or death from any cause, whichever occurred first. Overall survival (OS). 	

Objectives	Endpoints
Dose Expansion Phase (Phase 2)	
Primary	

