6.3.1 Primary Efficacy Analyses

Objective Response Rate (ORR)

Point estimate of the ORR will be provided for each study treatment and/or tumor indication with the 2-sided 80% and 95% exact Clopper-Pearson CIs (Clopper and Pearson 1934) and if an adequate number of responses are observed to warrant. Confidence intervals adjusting for the 2-stage nature of the design may also be provided.

The best overall response (confirmed CR, confirmed PR, SD, PD, NE) will also be tabulated to show the number and percentage of subjects in each response category.

ORR between the monotherapy and combination therapy cohorts of the same tumor type may be compared as an exploratory analysis. The difference and its 95% CI will be provided using the continuity corrected Wilson score method (Newcombe 1998). This analysis will be calculated only if an adequate number of responses are observed to warrant.

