6.3.2 Secondary Efficacy Analyses

Duration of Response (DoR)

DoR will be estimated using the Kaplan-Meier method along with the Kaplan-Meier plot if an adequate number of responses are observed to warrant.

The number and percentage of subjects who had events (response discontinued) or were censored will be summarized. The median, 25th percentile, 75th percentile, minimum and maximum will be provided along with the 95% CI for the median. The proportion and 95% CI for the number of subjects with durable responses at 6 months and 12 months from the onset of response will be provided. Other clinically relevant time points may also be included if data warrant.

Progression-free Survival (PFS)

PFS based on investigator assessments will be estimated using the Kaplan-Meier method and will be presented graphically if adequate data warrant. Censoring rules for the primary and sensitivity analyses are described in Table .

The number and percentage of subjects who had a PFS event or were censored will be summarized. The median, 25th percentile, 75th percentile, minimum and maximum will be provided along with the 95% CI for the median. The proportion and 95% CI for the number of subjects progression-free at clinically significant time points (e.g., 6 months, 12 months) from the date of the first dose will be provided. Other clinically relevant time points may also be included if data warrant.

Overall Survival (OS)

OS will be estimated using the Kaplan-Meier method along with the Kaplan-Meier plot if adequate data warrant.

The number and percentage of subjects who died or were censored will be summarized. The median, 25th percentile, 75th percentile, minimum and maximum will be provided along with the 95% CIs for the median. The proportion and 95% CI for the number of subjects alive at clinically significant time points (e.g., 6 months, 12 months) from first treatment will be provided. Other clinically relevant time points may also be included if data warrant.

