6.8.2 Exploratory Efficacy Analyses Based on iRECIST

If an adequate number of responses are observed to warrant, additional efficacy endpoints such as iORR, iDoR, iPFS based on iRECIST criteria may be analyzed similarly as their counterparts defined based on the RECIST criteria. For the iORR endpoint, iCR and iPR after iUPD will be included. For iDoR and iPFS, the event will be iCPD (confirmed PD) or death, whichever is earlier.

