8 CHANGES FROM PROTOCOL-SPECIFIED ANALYSIS

There are no changes from the analysis specified in protocol v8.0.

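### The SAP makes time-to-event analyses and the ORR confidence intervals depend on an undefined number of responses, so a low-response cohort could lose its ORR interval and its PFS and OS estimates

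*SAP*

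**What the plan says.** The condition appears in four places in the SAP, and the number of responses that would satisfy it is never given.

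- **SAP 6.1**, closing the paragraph on Kaplan-Meier methods for time-to-event data in general: "The time to event analysis will be calculated only if an adequate number of responses are observed to warrant".
- **SAP 6.3.1**: the ORR point estimate is to be given "with the 2-sided 80% and 95% exact Clopper-Pearson CIs (Clopper and Pearson 1934) and if an adequate number of responses are observed to warrant".
- **SAP 6.3.2**, for DoR: "DoR will be estimated using the Kaplan-Meier method along with the Kaplan-Meier plot if an adequate number of responses are observed to warrant".
- **SAP 6.8.2**: under the same condition, "additional efficacy endpoints such as iORR, iDoR, iPFS based on iRECIST criteria may be analyzed". SAP 2.2, Table 2, lists this Phase 1 secondary endpoint without condition: "Objective response rate (ORR) of confirmed complete response (CR) and partial response (PR) using RECIST v1.1 and iRECIST".

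Other text points the other way.

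- **Protocol 9.2.5** provides the Clopper-Pearson 80% and 95% intervals for ORR and a Kaplan-Meier summary of PFS, both without condition. For OS it says: "OS will be summarized using the Kaplan-Meier method".
- **SAP 6.1**, earlier in the same section, attaches 95% intervals to point estimates without condition.
- **SAP 6.3.2** ties PFS and OS to whether the data are adequate, not to a number of responses. It then promises event and censoring counts, medians with 95% intervals, and proportions at fixed times.
- **SAP 8**: "There are no changes from the analysis specified in protocol v8.0".

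**The concern.** A response count is the wrong condition for PFS and OS. SAP 4.2 starts both clocks at first dose. The PFS event is radiographic progression or death, and the OS event is death. A cohort without a single responder can supply every event these analyses need.

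It is also the wrong condition for an exact binomial interval. That interval can be computed at zero responses, and it is informative there because its upper limit shows which response rates the data still allow.

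The study is open-label and no number is fixed in advance, so whoever judges adequacy will already know the responses. Whether a cohort's results are printed could then depend on how good they are. If PFS and OS were shown only for cohorts with responses, the reported estimates would be a set selected on outcome. PFS and OS stand among the Phase 2 primary endpoints in the objectives tables of both documents, and among the Phase 1 secondary endpoints.

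**Working it through.** **1. The plan's own design figure.** Inputs from Protocol 9.4 and SAP 2.3: 16 subjects in Stage 1, continue if at least 2 respond, 31 in total, promising if at least 6 respond, null rate 10%, alternative 25%.

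P(promising | p) = Σ over x = 2 to 16 of P(Bin(16, p) = x) × P(Bin(15, p) ≥ 6 − x)

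- At p = 0.25: 0.805, against the stated power of 80%.
- At p = 0.10: 0.079, within the stated limit of 0.1. The gap is the usual discreteness of an exact design.

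The design reproduces, and nothing in this point changes it.

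**2. How often a cohort has very few responses in Stage 1.** P(0/16) = (1 − p)^16 and P(1/16) = 16p(1 − p)^15. The 5% rate is an assumption, chosen to show a less active cohort.

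| True ORR | P(0/16) | P(at most 1/16) |
|---|---|---|
| 5% (assumed) | 44.0% | 81.1% |
| 10% (null) | 18.5% | 51.5% |
| 25% (alternative) | 1.0% | 6.3% |

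At 10%, P(1/16) = 51.5% − 18.5% ≈ 33%, so a single response is the commoner result among cohorts that stop.

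**3. What the interval would show.** For 0/16 the Clopper-Pearson upper limit is 1 − (α/2)^(1/16):

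- 95%: 1 − 0.025^(1/16) = 20.6%
- 80%: 1 − 0.10^(1/16) = 13.4%

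For 1/16 the upper limit solves (1 − p)^16 + 16p(1 − p)^15 = α/2.

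| Result | 80% interval | 95% interval | Excludes 25%? |
|---|---|---|---|
| 0/16 | 0 to 13.4% | 0 to 20.6% | both levels |
| 1/16 | 0.7 to 22.2% | 0.2 to 30.2% | 80% only |

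**4. Which analyses need responders.**

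| Analysis | Needs responders? | Protocol 9.2.5 | SAP condition |
|---|---|---|---|
| ORR intervals | no | unconditional | responses (6.3.1); 6.1 also attaches 95% intervals without condition |
| PFS | no | unconditional | responses (6.1); adequacy of data (6.3.2) |
| OS | no | unconditional | responses (6.1); adequacy of data (6.3.2) |
| DoR | yes | among responders | responses (6.1, 6.3.2) |
| Phase 1 iRECIST ORR | no | no separate analysis given | responses, and optional (6.8.2) |

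Only DoR has a natural reason for a response condition.

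**The case against.** **The endpoint-specific text is milder.** For PFS and OS the response condition rests on one general sentence in SAP 6.1. In 6.3.2 the condition concerns data, and for PFS it can be read as limiting only the plot. A reader might infer that a negative cohort will certainly show no PFS or OS. The documents do not support that: 6.3.2 promises medians and intervals, and the two sections conflict. The conflict stands and needs resolving.

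**The ORR information is not destroyed.** Best overall response is tabulated without condition, so anyone with the responder count and the denominator can compute the exact interval. The clause in 6.3.1 is also badly formed and may be an editing slip. That lessens the harm. But the protocol promises the interval itself, and under SAP 6.1 a zero count is printed without a percentage.

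**The probabilities do not measure the condition.** A reader might take 51.5% as the chance that results are withheld. It is the Stage 1 stopping probability at a 10% response rate, and no text links the condition to that boundary. Nor would an omitted interval always rule out the 25% target: at 1/16 the 95% interval does not.

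**A condition on DoR is reasonable**, because DoR is defined only among responders. It is not part of the fault.

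**The SAP may add detail.** Protocol Section 9 describes itself as a summary, and SAP 1 requires only major modifications to be documented. SAP 4.2 and 6.3.2 also treat PFS and OS as secondary, despite the Phase 2 primary listing in Table 2. Whether a condition on reporting is a major modification can be argued. Making a promised estimate optional is more than added detail, though, so the statement in SAP 8 is hard to sustain as written.

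**Conclusion.** The point holds as a conflict in the text with a possible consequence. Read literally, SAP 6.1 and 6.3.1 allow a cohort's ORR intervals and its Kaplan-Meier PFS and OS to be left out because too few responses were seen. The protocol promises these results unconditionally, and other SAP sentences agree with the protocol. A low-response cohort could lose them; nothing shows that it would.

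How often this would happen cannot be computed, because no threshold exists. The 18.5% and 51.5% at a true ORR of 10% show only how common very low Stage 1 counts are. They assume that all 16 subjects are evaluable and respond independently with the same probability. Sample size, power and type I error are unaffected.

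The iRECIST question is related but separate. An endpoint listed as secondary for Phase 1 is handled in the SAP as exploratory and optional, and SAP 8 does not declare this. The correction should be made, since it costs little and keeps reporting from depending on the result.

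**What to change.** - **SAP 6.1:** limit the response condition to DoR, preferably with a stated minimum number of responders.
- **SAP 6.3.1:** delete the condition, so that ORR with exact 80% and 95% intervals is always reported, including at zero responders.
- **SAP 6.3.2:** state that Kaplan-Meier PFS and OS are always reported. If a condition on the plot is wanted, word it so that it covers only the plot.
- **SAP 6.8.2:** report Phase 1 iRECIST ORR as the listed secondary endpoint, or declare its move to exploratory in SAP 8.
- **SAP 8:** declare any condition that is deliberately kept and departs from Protocol 9.2.5.

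The cost is SAP wording and a few extra tables. No further data collection is needed, and the design does not change.

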6.2 Subject Characteristics and Disposition

The safety population will be used for all tables and listings.

6.2.1 Subject Disposition

Subject disposition will be summarized in terms of counts and percentages for all subjects who have signed the informed consent regardless of study treatment. The following subject disposition categories will be summarized:

- Subjects consented
- Subjects consented but not treated (screen failure)
- Subjects treated with E-602 and E-602 + cemiplimab
- Subjects discontinued E-602 and E-602 + cemiplimab
- Subjects discontinued the study
- Subjects completed the study (end of study reason from the Case Report Form [CRF])

For subjects who discontinued study treatment or discontinued the study, a summary will be provided by reason of discontinuation.

The number and percentage of subjects in each defined analysis population will be tabulated. Individual listings will be generated for the screen failures and safety populations.

6.2.2 Protocol Deviations

Protocol deviations will be identified and reported following the process described in the Protocol Deviation Plan. Important protocol deviations considered reportable in the CSR per the Protocol Deviation Plan will be summarized and listed by subject.

The number and percentage of subjects with CSR reportable protocol deviations will be summarized by dose/cohort and overall, for all treated subjects. Protocol deviations will be classified by CSR reportability prior to database lock.

A subject listing with all deviations will be provided.

6.2.3 Demographics and Baseline Characteristics

Demographic characteristics such as age at consent, sex at birth, race, and ethnicity will be summarized. Age will also be categorized as <65 vs ≥65. Baseline height (cm), body weight (kg), and Eastern Cooperative Oncology Group (ECOG) performance status will be summarized using frequencies and percentages.

Demographics and baseline characteristics will be listed by subject.

6.2.4 Medical History

Medical history will be collected during Screening. All pertinent prior medical conditions, surgeries or other medical procedures, allergies, and medications will be collected.

The reported medical history terms may be coded using MedDRA v24.1 or later. Medical history will be summarized by system organ class (SOC) and preferred term (PT).

Frequencies and percentages of subjects reporting each PT will be presented by SOC and PT. For each subject, multiple events of the same PT will be counted once in the summary. All reported medical history data including those with incomplete dates will be included in the analysis.

Reported medical history data will be presented in a by-subject listing.

6.2.5 Cancer History

Cancer history will be collected during Screening. Time since initial diagnosis (days) (Cycle 1 Day 1 [first dose study drug] – date of initial diagnosis) +1 and time since most recent progression (days) (Cycle 1 Day 1 [first dose study drug] – date most recent progression) +1 will be summarized with descriptive statistics. Categorical variables, including primary cancer type, tumor stage at time of initial diagnosis, histology/cytology, grade, and tumor stage at study entry, will be summarized using frequencies and percentages.

Cancer history data will be presented in a by-subject listing.

6.2.6 Prior Cancer Therapies

For systemic anti-cancer treatments, the number of prior lines of treatment received will be summarized. The reported cancer therapy terms will be coded using the World Health Organization (WHO) Drug Dictionary (September 2021 or later). Prior cancer therapies will be summarized by Anatomical Therapeutic Chemical (ATC) and preferred name. A subject will be counted only once within an ATC classification but may contribute to two or more preferred names in the same classification.

The number and percentage of subjects who received prior radiation therapy and prior cancer surgery will be summarized.

All prior therapies will be listed, including prior systemic anti-cancer treatments (preferred name by ATC and verbatim term), prior radiation therapy, and prior cancer surgery.

